7.9. Enrollees May Drop Out

Participants may voluntarily withdraw from participation at any time, for any reason, with no penalty or loss of rights. The reasons for drop-out and missing data will be documented in/with the database. If a participant wishes to withdraw from the intervention conditions, we will ask if they remain willing to complete the self-report surveys, particularly the irritability symptom scale on a daily basis, throughout the remainder of time that would correspond to their 14 study visits as irritability symptoms is the primary outcome variable.

8. Statistical Analysis Plans

8.1. Strategies that Apply to all the Aims

The statistical analysis plan was developed in collaboration with [name], biostatistician for the Department of Psychiatry. [name] will perform the analyses for this protocol under the supervision of [name]. Participant flow will be tracked and reported using the CONSORT flow diagram and recommendations for cross-over study designs. The following baseline predictors will be calculated to model outcome variables: baseline irritability (sum of 5-items on the III Temper scale of the IDAS), E1G variability (standard deviation of 14 every-other-day E1G collections), and neurophysiological (EEG) correlates of threat and frustration (e.g., theta and beta oscillatory activity, event-related potentials (ERPs)) during the Dot Probe and Affective Posner Paradigm EEG tasks. Statistical estimates of population parameters will be estimated and tabulated using the statistical models

described in statistical plan of specific aims, along with corresponding confidence intervals and standard errors to indicate precision. All hypothesis tests yielding large p-values will be reported as being inconclusive. All the p-values will be reported with 3 decimal places to indicate the accuracy. The outcome of the proposed study will be discussed within the study team and outcome-dependent exploratory analysis will be designed and performed to generate new hypothesis if it is deemed necessary by the team. We acknowledge that no p-value can reveal the plausibility, presence, truth, or importance of an association or effect. All the response outcomes will be visualized using either boxplots by treatment or scatterplots between predictors and outcomes.

We will conduct a sensitivity analysis with and without missing data by assessing the following: 1) point estimates from complete cases, and 2) mean imputed values based on the observed data.

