5. A history of E2 dependent neoplasia **6.** A history of liver dysfunction 7. A personal or family history suggesting elevated risk for E2-related cancer or thrombotic events 8. Use of psychotropics or hormonal agents **9.** A history of psychosis or bipolar disorder **10.** Suicidality with intent **11.** Current mood disorders of severity to require treatment A total of N = 50 eligible individuals will be enrolled. Based on our prior Numbers of Enrollees studies of TE2, of the estimated 50 women who pass our phone screening and come to an in-person enrollment, we predict that 30% (n=15) will not meet eligibility for TE2 after personal and family history review or will not meet reproductive staging criteria based on further detailed questions about their menstrual bleeding patterns. We anticipate that up to an additional 15% (n =5) may withdraw after enrollment, yielding 30 women who we anticipate will complete all aspects of the protocol and will have complete data. Up to 135 individuals will be recruited and screened. 40% will fail the screening for TE2 eligibility, and an additional 20% will not be interested in participating. Using a within-subjects, cross-over, placebo-controlled, double-blind Interventions or design, participants will be randomized (1:1) to either three weeks of **Exposures/Conditions** transdermal E2 (0.1 mg/day) or to three weeks of transdermal placebo as their first condition (Condition 1). Weekly mood ratings and daily ill temper (irritability) ratings will be collected across the three weeks. In week 3 of each Condition, daily E1G collections will commence (days 15-21) and the EEG session with Dot-Probe and Affective Posner Paradigm tasks will be administered (day 21). A three-week washout period will follow. Condition 2 (3 weeks) will follow the washout (placebo E2 if Condition 1 was active E2 or active E2 if Condition 1 was placebo) with identical assessments and timeline as for Condition 1. To prevent TE2-induced endometrial hyperplasia, 200 mg micronized progesterone/day for 10 days will be given to all women at study completion (Progesterone follow-up phase). **Outcome Measures** For Aim 1. Over the four-week baseline period, irritability symptoms will be measured daily using the III temper subscale of the Inventory of Depression and Anxiety Symptoms (IDAS). Urinary measures of E1G will be collected every other day (14 samples total) and assayed using an enzyme immunoassay (Arbor Assays, Ann Arbor, MI), with sensitivity at < 22.5 pg/mL to calculate within subject fluctuation in E1G (indexed by the standard deviation of E1G over the four weeks). At the end of baseline week 4, Theta and Beta oscillatory frequencies will be assessed at rest and in response to the Dot Probe task which measures attention bias to angry faces (threat attention bias) and in response to the Affective Posner Paradigm that measures relational aggression (approach behavior) in response to frustration. For Aim 2. The outcomes are identical to those in Aim 1. The primary comparison will be within subject - comparing the active TE2 condition

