
Statistical Analysis Plans for Each Aim Study Duration	to the placebo TE2 condition. Irritability symptoms will be measured daily using the III temper subscale of the Inventory of Depression and Anxiety Symptoms. Theta and Beta oscillatory frequencies will be assessed at rest and in response to the Dot Probe task and the Affective Posner Paradigm administered at the last day of each condition. Urinary measures of E1G will be collected every day during the last week of each condition and measured using an enzyme immunoassay (Arbor Assays, Ann Arbor, MI), with sensitivity at < 22.5 pg/mL to generate to within subject variability in E1G (indexed by the standard deviation of E1G). Aim 1 Plans. Linear regression models will predict irritability symptoms and theta and beta frequencies in response to tasks from E1G variability (based on the standard deviation of seven daily E1G measurements) and predict irritability symptoms from theta and beta task-related frequencies. Aim 2 Plans. The two repeated post-treatment EEG measures (theta and beta task-related frequencies) will be modeled as a function of fixed factors including baseline EEG measures (continuous), Condition status (TE2 or placebo; binary), and order of Condition (binary) in a linear mixed effects model with a random intercept accounting for the within-subject variance. The two-sided Wald test will test the significance of TE2 effects. 2b) Similarly, daily irritability symptoms (3 weeks/Condition) will be modeled as a function of fixed factors including baseline irritability symptoms (continuous), Condition, and order of Condition in a linear mixed effects model with a random intercept accounting for within-subject variance.
Participation Duration	Sixteen weeks
Enrollment Duration	Two years

2. Introduction

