Define the baseline relationships between: (a) E1G variability and irritability symptom severity; (b) E1G variability and theta and beta oscillatory correlates of threat and frustration; (c) irritability symptoms and theta and beta oscillatory correlates of threat and frustration. The estimands of interest are the correlation coefficients between a) E1G variability (standard deviation (SD) of E1G over the four-week baseline phase) and irritability symptoms b) E1G variability (SD) and theta and beta oscillatory activation during threat and frustration tasks; and c) irritability symptoms and theta and beta oscillatory activation during threat and frustration tasks.

3.2. Aim 2

Determine whether TE2, versus placebo, will: a) beneficially modify task-evoked theta and beta oscillations (i.e., reduce theta and increase beta activation) in response to threat and frustration tasks; and b) reduce irritability symptom severity. The estimands of interest are a) the mean difference (and direction of difference) between the active TE2 and placebo TE2 conditions in theta and beta activation to threat and frustration tasks and b) the mean difference (and direction of difference) between the active TE2 and placebo TE2 conditions in mean irritability symptom severity.

4. Study Design

This single site, interventional study employs a within-subjects, cross-over, placebo-controlled, double-blind design.

Stage 1: A four-week baseline assessment involving: 1) at home urine collections of E1G; 2) mood ratings (general mood and irritability specific ratings); and 3) in-lab EEG session to assess theta and beta oscillations in response to behavioral tasks designed to elicit threat reactivity (Dot Probe task) and frustration to non-reward (Affective Posner Paradigm). Four weeks was chosen to allow for a sufficient number of E1G collections (n=14) to calculate a reliable standard deviation score for each participant.

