4.3. Measurement Design

Table 1. Variables of interest: their occasions of evaluation, their uses for the aims, their roles in the study

Variables within Domains	Scale ¹	Visits ²	Aims	Main Roles
Identifiers				
Participant ID	nominal	all	all	identifier
Screening Profile				
systolic blood pressure (SBP)	mmHg	0, 5-7, 11-13	N/A	screening and safety
diastolic blood pressure (DBP)	mmHg	0, 5-7, 11–13	N/A	screening and safety

body mass index (BMI)	kg/cm ²	0, 7, 13	N/A	screening and safety
age	decimal yrs	0	N/A	screening
Life Events Survey	binary	0	N/A	screening
Psychiatric history	categorical	0	N/A	screening
Medical and cancer history	binary	0	N/A	screening
Reproductive Stage	binary	0	all	screening
Research Lab Assays				
Urinary E1G	pg/ml	1-4, 7, 13	Aim 1	predictor
EEG (theta and beta) oscillatory activation	dB	4, 7, 13	all	primary outcome
Patient-Reported Outcomes				
Daily self-reported irritability	continuous	1 – 13	all	primary outcome
Behavioral inhibition/Activation Scale (BIS/BAS)	continuous	4, 7, 13	Aim 2	secondary outcome
Frustration to non-Reward Scale	continuous	4, 7, 13	Aim 2	secondary outcome
Green Climacteric Scale	continuous	0, 4, 7, 13	all	covariate
Pittsburgh Sleep Quality Index	continuous	0, 4, 7,13	all	covariate
Safety Monitoring				
AEs and SAEs documentation	events	0, 4-13	N/A	safety monitoring

¹Units of measurement or the scale.

Screening Measures:

Blood pressure will be taken at baseline to confirm eligibility (< 160/100 mmHg) based on a minimum of three stethoscopic blood pressures taken by a trained research staff member. Participants will be seated comfortably for a minimum of five minutes prior to the first reading with arm supported on a table. Assessments will be at least one minute apart. A mean systolic and diastolic pressure (SBP and DBP) will be derived based on the three readings. Participants must have a resting SBP <160 and a resting DBP <100 mmHg to continue in the research. The same BP protocol will be used at study visit 5-7 and 11-13 to ensure the participant remains normotensive.

Body Mass Index will be derived based on height and weight measured by a research assistant in the laboratory using the Health-o-meter (Professional) scale. BMI will be calculated using the formula: weight in kg/height in m²

Age will be determined by self-report.

Reproductive Stage will be initially determined by phone and confirmed in the enrollment session based on self-report of bleeding patterns.

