EEG Data Acquisition and Processing. A 32-channel actiCAP will be positioned according to the 10-20 system, with a Brain Products actiCHamp Plus amplifier. Preprocessing and analysis of EEG data will be performed using custom MATLAB scripts and the EEGLAB processing toolbox. EEG will be digitally re-referenced to the average reference, high pass filtered at 1.0 Hz, and epoched from -1 to 2 seconds to accommodate time-frequency analyses. EEG epochs containing amplitudes >100 μV at any scalp electrode with abnormally distributed data will be rejected. All cleaned, epoched data will be loaded into an EEGLAB STUDY mechanism to compute the time-frequency transform using the 'newtimef' 3-cycle wavelet function to yield Time X Frequency spectrograms. Theta (4-8Hz) and beta (13-30Hz) will be extracted from the pre-computed matrices at frontal (Fz) and parietal (Pz) midline electrodes.

E1G Assessments. We will use the same E1G assay and methods as Gordon et al,¹ who showed that variability in urinary E1G reliably identified perimenopausal women for whom *changes* in E1G predicted depression symptom severity. Week-to-week changes in E1G also differentiated women based on the direction of E1G change (i.e., increasing vs. decreasing levels) and symptom severity. The first morning voided urine will be used for measuring E1G, reflecting an integrated measure of overall E1G level from the previous day, and correlating very highly with serum E2 (r= 0.93).⁴0 At the end of each collection week, research staff will retrieve samples (stored in home freezer) and bring to our lab for storage at -80°C. Urinary E1G is not affected by the repeated freezing and thawing of specimens,⁴0 E1G will be assayed using an enzyme immunoassay (Arbor Assays, Ann Arbor, MI), with sensitivity at < 22.5 pg/mL. The specificity is high, with £ 0.1% cross-reactivity with similarly structured compounds, though cross-reactivity with E2 is higher at 5%. Since this research is focused on within person variation and we are using E1G as an indicator of E2 serum levels, any cross reactivity with E2 will not affect interpretability of our findings. The intra-assay variability = 4-6% and the inter-assay variability = 4-7%. Although there is little evidence to date that sensitivity to progesterone is a risk factor for affective impairment in the MT,¹ pregnanediol-3-glucuronide (PDG; a metabolite of progesterone) is assessed simultaneously with E1G and can be used as a covariate in analyses.

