8.3. Aim-Specific Plans

Plans for Aim 1. The objective of Aim 1 is to define baseline relationships between E1G variability, irritability symptom severity and neurophysiological correlates of threat and frustration (e.g., theta, beta, and associated ERPs (continuous)). Linear regression models will predict irritability symptoms and EEG variables from E1G variability (3) and predict irritability symptoms from EEG measures (2).

Plans for Aim 2. The objective of Aim 2 is to determine whether TE2, versus placebo, will beneficially modify EEG variables and reduce irritability symptom severity. Normality assumption will be accessed using studentized residual and extreme outliers will be assessed individually.

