Aim 2a) The two repeated post-treatment EEG measures (theta, beta, ERPs) will be modeled as a function of fixed factors including baseline EEG measures (continuous), Condition status (TE2 or placebo; binary), and order of Condition (binary) in a linear mixed effects model with a random intercept accounting for the within-subject variance. The two-sided Wald test will test the significance of TE2 effects. 2b) Similarly, weekly irritability symptoms (3 weeks/Condition) will be modeled as a function of fixed factors including baseline irritability symptoms (continuous), Condition, and order of Condition in a linear mixed effects model with a random intercept accounting for within-subject variance. Although we hypothesize that E1G variability will predict outcomes in Aim 1 and Condition effects in Aim 2, we will examine E1G levels if analyses do not support variability. In the statistical models described above, all the estimates of treatment effect, along with 95% confidence interval will be reported in the tabulated forms. Whenever multiple testing is used in the analysis described, Benjamini-Hochberg Procedure will be used to adjust for multiple comparison. All the hypothesis tests that yield large p-values will be reported as being inconclusive. To evaluate the robustness of the proposed study, we will perform sensitivity analysis for all the important findings. More specifically, we will repeat all the statistical analysis by excluding some potential outliers that could be influential points. We expect the sensitivity analysis will preserve the direction of original point estimates from full samples. Based on the study design, there will be potential missing data points caused by subject drop-out, and we assume all the missingness will most like to be missing at random (MAR). Since the linear mixed effects model is capable of handling missing values, the analysis plan will not be affected because of missing data.

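### Aim 1 indexes E1G variability by an unscaled SD and leaves mean E1G out of the models; if variation is proportional to level, fluctuation and level cannot be separated

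*Combined protocol and SAP*

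**What the plan says.** The index is a plain standard deviation wherever it is defined. Section 8.1 has "E1G variability (standard deviation of 14 every-other-day E1G collections". Section 3.1 has "E1G variability (standard deviation (SD) of E1G over the four-week baseline phase". The Synopsis outcome measures say "indexed by the standard deviation of E1G over the four weeks". The Synopsis Aim 1 plan differs on the number of values, "based on the standard deviation of seven daily E1G measurements", but it is still an unscaled SD. Table 1 in section 4.3 lists "Urinary E1G pg/ml 1-4, 7, 13 Aim 1 predictor", so the values are concentrations.

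The Aim 1 model is in section 8.3: "Linear regression models will predict irritability symptoms and EEG variables from E1G variability (3) and predict irritability symptoms from EEG measures (2". Mean E1G is not named as a covariate. The only hormone covariate mentioned anywhere is PDG, as an option in section 4.3. Level enters later in 8.3, as a fallback: "we will examine E1G levels if analyses do not support variability".

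**The concern.** The study's central claim is susceptibility to estradiol fluctuation, and section 8.3 itself names level as what to look at if fluctuation does not explain the outcomes. For that sequence to be informative, the variability index must not be largely a measure of level. An SD in concentration units is one whenever swings scale with the mean: a woman with twice the E1G and the same relative fluctuation has twice the SD.

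The fallback is also one-directional. If the SD slope is significant, nothing in the plan commits to asking whether mean E1G explains it. If it is not significant, a real effect of relative fluctuation may have been diluted or offset by differences in level. Differences in level between participants are plausible, because section 2.1 describes a declining estradiol trend across the transition and section 5.2.1 admits both early- and late-stage women.

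**Working it through.** **1. The plan's own figure.** Section 9 gives more than 95% power for Aim 1 at N = 30 and f = 0.69.
- R² = f²/(1 + f²) = 0.4761/1.4761 = 0.3225, so r = 0.568.
- Noncentrality = N f² = 30 × 0.4761 = 14.28, with 1 and 28 degrees of freedom.
- Two-sided alpha is assumed to be 0.05, since none is stated. Power is 95.4%, which reproduces the plan's figure. A Fisher z approximation gives 91.8%.

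This figure takes the index to be the quantity that carries the effect. The remaining steps ask what happens when it is not.

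**2. Why the SD follows level.** Write a woman's E1G on one day as L·exp(s·z), where L is her usual level, s her relative variability and z standard normal. Then:
- mean = L·exp(s²/2)
- raw SD = mean × √(exp(s²) − 1), that is, mean × CV
- SD of log E1G = s

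Doubling L doubles the raw SD and leaves the log-scale SD unchanged.

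**3. Simulation inputs.** From the documents: N = 30 and 14 values per woman. Assumed, because the documents give no E1G distribution:
- log-normal E1G
- between-woman SD of log E1G of 0.3, 0.5 or 0.7
- typical within-woman CV of 0.3 or 0.6
- spread of that variability across women (log SD) of 0.1, 0.3 or 0.5
- an outcome that depends on level only, with correlation 0.5
- a single two-sided test at 0.05

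**4. Results when only level matters.** Each cell is the percentage of trials with a significant raw-SD slope (5,000 trials per cell).

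| Between-woman SD of log E1G | Within-woman CV | Spread 0.1 | Spread 0.3 | Spread 0.5 |
|---|---|---|---|---|
| 0.3 | 0.3 | 50.7 | 30.6 | 15.4 |
| 0.3 | 0.6 | 36.9 | 18.5 | 9.8 |
| 0.5 | 0.3 | 64.1 | 48.5 | 28.6 |
| 0.5 | 0.6 | 55.0 | 33.8 | 16.7 |
| 0.7 | 0.3 | 67.2 | 55.6 | 37.5 |
| 0.7 | 0.6 | 61.0 | 42.7 | 22.5 |

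The range is 9.8% to 67.2%. The median of the 18 cells is (36.9 + 37.5)/2 = 37.2%. In the same cells the SD of log E1G, the CV, and the log of the raw SD adjusted for mean log E1G are each significant in about 5% to 6%. The median correlation of the raw SD with a woman's observed mean E1G runs from 0.64 to 0.94.

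**5. Sensitivity to the strength of the level effect.** A second set-up has within-woman log SD uniform on 0.3 to 0.7 and between-woman log SD of 0.3 / 0.5 / 0.7. At correlation 0.5 the raw SD is significant in about 28 / 46 / 54% of trials. At correlation 0.3 this falls to about 13 / 18 / 23%.

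**6. Sign.** In that second set-up at correlation 0.5, if lower level goes with more irritability, significant positive slopes occur in about 0% of trials and the 28 / 47 / 54% that are significant are all negative.

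**7. Cost to the plan's own hypothesis.** Suppose true relative variability drives the outcome at r = 0.568 (f = 0.69), with mid-range assumptions (between-woman log SD 0.5, CV 0.5, spread 0.3). Power is then 32% with the raw SD and 76% with the log-scale SD.

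**8. Null check.** With neither a level nor a variability effect, the raw SD rejects in 5.0% of trials.

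**The case against.** Four objections have force.

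- **The raw SD is a legitimate quantity.** Absolute fluctuation is a coherent target. The log-scale SD answers a different question, about relative fluctuation, and gives more weight to low values. This stands, and it is why the raw SD need not be replaced.
- **The size is assumption-driven.** Proportional variation is not documented. Section 4.3 gives only assay imprecision in percent (4-6% and 4-7%), so only that small part of the SD scales with level on the documents' own figures. This stands, so the result has to be quoted as a range.
- **The sign may run against the hypothesis.** Section 2.1 describes falling estradiol, and the Synopsis expects a treatment that raises levels to reduce irritability. Both suggest that low E1G goes with more irritability. The raw-SD slope would then be negative, which could hardly be presented as support for fluctuation. This stands: in that direction the harm is masking or reversal.
- **Other checks are possible.** Section 8.1 allows exploratory analyses that depend on the results, and section 4.3 imports a cited study's assay and methods. Neither commits the trial to checking a variability finding against level.

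A reader might also infer that urine dilution makes a creatinine assay necessary. The documents do not support that as a requirement. Section 4.3 says "The first morning voided urine will be used for measuring E1G", which lessens dilution differences, and the imported methods cannot be seen. Section 11.4 has cards discarded once assayed, and nothing in the documents supports a cost for a further assay.

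**Conclusion.** The concern holds in a limited form. Aim 1, as written, cannot separate fluctuation from level if within-woman variation is roughly proportional to level. On that assumption, with N = 30 and a level-outcome correlation of 0.5, a pure level effect yields a significant raw-SD slope in roughly 10% to 67% of trials, against about 5% for the log-scale SD. The rate is smallest when women differ much more in relative variability than in level, and it is lower for weaker level effects. These are unadjusted single-test rates; the Benjamini-Hochberg step in 8.3 was not modelled and could only lower them.

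Three stronger readings are not supported:
- That false positives are inflated in general. The null rejection rate is 5.0%, so the fault is misattribution.
- That the title and aims set level against variability. Only the fallback sentence in 8.3 does so.
- That the randomised comparison in Aim 2 is compromised. Its models contain condition, order and the baseline outcome, not the E1G index.

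**What to change.** In sections 8.1 and 8.3:
- Keep the raw SD, and pre-specify that every Aim 1 E1G analysis is also run with the within-woman SD of log E1G, or with the log of the SD adjusted for mean log E1G, whatever the raw-SD result.
- Report the correlation of the raw SD with mean E1G.
- State that an association will be attributed to variability only if it persists on the level-free index.

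The number of values entering the SD (14 or seven) should be reconciled in the same edit.

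The cost is one more analysis per model on data already planned, results on a relative scale rather than in pg/ml, and one degree of freedom (28 to 27 at N = 30) if the adjusted form is used. No new samples or assays are needed.
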